#### 13.5 Follow-up

All outcomes will be assessed after randomisation and intervention delivery (baseline) and 18 months later.

#### 14 Statistical considerations

#### 14.1 Sample size

The total sample size of 12 schools for the exploratory trial is anticipated to equate to approximately 2040 students (assuming a 170 pupils in a year), which with a response rate of 90% (based on 1-year follow-up in the RCT of ASSIST (10), will achieve a sample of 1632 students (408; 408; 408 per arm). If the average year group had 150 students, we would expect 1800 to be sampled; 1440 respond with an 80% response rate, equating to 360 per arm. The choice of 12 schools will provide some information on variability within and between schools at baseline and follow-up. This sample is not anticipated to provide adequate

power to detect a statistically significant difference across groups, as this is an exploratory trial. However, the sample will indicate the likely response rates, and permit estimates (with 95% confidence intervals) of likely effect sizes, and intra-cluster correlations (ICCs) of drug incidence in each group in anticipation of a larger trial.

## 15 Analysis

### 15.1 Main analysis

The statistical analyses will be primarily descriptive, providing a realistic estimate of eligibility, recruitment, intervention delivery and retention rates in the study population. We will analyse key secondary outcomes that are more immediate targets of the intervention (e.g. knowledge of the harms of drug use; mean peer level drug use) to consider the potential of the intervention. We will undertake mediator analysis to see if the identified pathways in the logic model are associated with the uptake of drug use. Individuals lost to follow-up will be compared to those who complete follow up to identify any potential biases.

An intention to treat (ITT) analysis will compare the prevalence of any drug use across the 4-arms using a two-level logistic regression model to account for clustering within schools. The main analysis will examine prevalence of any drug use at 18 months. The baseline prevalence of any drug use, as well as age, sex, free school meal entitlement, and family affluence will be included as covariates. As an exploratory trial the proposed analysis is not powered to provide a definitive comparison between the intervention and control groups and as such p-values will not be presented. An exploratory analysis will nevertheless be undertaken. We will model comparisons between: a) ASSIST and the usual care control (to examine any unintended effects of ASSIST on drug use), b) ASSIST+Frank and the usual care control, c) Frank friends and the usual care control, and d) ASSIST and ASSIST+Frank to estimate the added value of the Talk to Frank content. These key trial parameters will inform the power calculations for a future definitive trial.

Between-group comparisons for secondary outcomes will be modelled similarly using either linear (e.g. frequency of drug use) or logistic (e.g. cannabis dependence) regression models with the focus on 95% confidence intervals to estimate possible effect sizes.

Exploratory analysis will consider the impact of demographic factors as well as other theoretical moderators on the intervention effect using interaction terms included in the main

analysis models. We will model interactions between potential intermediary factors (e.g. changes in: the perceived prevalence of drug use within the year group, knowledge on the harms of drug use, methods of help seeking, frequency of drug use offers, and attitudes towards heavy drug use and drug dependency, adolescent mental health (Short mood and feelings questionnaire (22)); school engagement (using the Beyond Blue 'School climate' scale(23)), attitudes towards heavy drug use, average level of drug use amongst peers; and average level of drug use amongst peer-leaders) and allocation to: ASSIST+Frank vs. usual care; Frank friends vs. usual care; ASSIST vs. usual care; and ASSIST vs ASSIST+Frank. It is acknowledged that any interactions are unlikely to be adequately powered to provide precise estimates, but 95% confidence intervals will indicate the feasible effect sizes in a full trial.

Analysis will be conducted using Stata v.11 (26) and R statistical packages (27).

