A three-arm RCT of the Towards No Drug Abuse (TND) programme (8), examined the additional benefit of adding a peer-led review of intervention materials at the end of 12 sessions delivered by teachers (3). TND emphasises improving education on the risks of drug use, decision making and self-control. High-school classes (n= 840 students; mean age 16) were randomized to: a) standard TND curriculum; b) standard TND curriculum with a peerled component (TND-Network); a control. Peer-leaders were those receiving the most nominations regarding "who would make the best leaders for a project in class". Groups were then created within each class by assigning students to a leader whom they had chosen, or to whom they were socio-metrically closest (9). Compared with controls, students in the TND arm did not report a significant change in their drug use, but those in the TND Network arm reported a reduction in the frequency of cannabis and cocaine use in the past month at a one year follow-up. An interaction between allocation to TND-Network vs. control arm and peer substance use (i.e. the average use of tobacco, alcohol, cannabis and cocaine reported by the five classmates nominated as friends) revealed that the intervention was most effective for students embedded in peer networks that did not engage in substance use. Those students with friends who had already used substances in the TND-network arm were more likely to increase their use suggesting the potential for harms via the diffusion of pro-drug norms in poorly designed peer-led interventions. However, contamination is a major methodological weakness in this trial which allocated classes (rather than year group or schools); therefore the effect of TND network in this comparison may have been diluted (3).

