#### **8.3** Pilot secondary outcome measures

Using the example questions proposed by the European Monitoring Centre for Drugs and Drug Addiction (EMCDDA) (14), those used in the ALSPAC study (15), the most recent Health and Social Care Information Centre report on Smoking, Drinking and Drug Use Among Young People in England, (16) and the Eu-Dap trial (17) we will evaluate the effect of the interventions on:

Use of cannabis, cocaine, amphetamines, crack, ecstasy, aerosols, gas, glue, solvents,
 poppers, nitrus oxide, sedatives or sleeping Pills, LSD, magic mushrooms, ketamine,

steroids, methadrone, other prescription drugs, and opioids. Questions will assess use: ever (lifetime prevalence), over the 12 months, past 30 days and past week (15);

- Age of first experimentation with any drug;
- Cannabis use: age of first use; frequency of use; symptoms after use (e.g. anxiety, relaxation, paranoia); method of use (by itself, mixed with tobacco) (15); cannabis dependence: Cannabis Abuse Screen Test (CAST; (18) (19));
- Tobacco use: lifetime use; current use; use in past 12 months, past 30 days and past week; frequency of use; (taken from ASSIST trial (10) and Health Survey for England (20)); Heaviness of Smoking Index; Fagerstrom test of nicotine dependence (21);

We will also collect data on attitudinal and knowledge based precursors to drug use to explore potential mediators of the effect of ASSIST+Frank and Frank friends on drug use. These include the perceived prevalence of drug use within the year, knowledge on the harms of drug use, methods of help seeking, frequency of drug use offers, and attitudes towards heavy drug use and drug dependency, adolescent mental health (Short mood and feelings questionnaire (22)); school engagement (using the Beyond Blue 'School climate' scale (23)), and records on educational achievement. These intermediate outcomes will be used to explore potential mechanisms, such as drugs literacy, drug use norms and peer communication.

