#### 13.4 Data collection

Baseline and 18-month follow-up self-report questionnaires will be completed under 'exam conditions'. To minimise the burden on staff and students, two members of the research team and two fieldwork staff will attend baseline and follow-up surveys. All research staff involved in collecting data will be subject to a clean Disclosure and Barring Service check (DMB; previously a Criminal Records Bureau check). As far as possible they will be blinded to the allocation of the participants, although during interaction with them the group allocation may become apparent. Where this occurs it will be recorded. Data collection at each time point will take around 40 minutes. At the end of each data collection a list of absent students will be prepared and an additional data collection arranged with a school contact (typically the head of year).

Interviews and focus groups will be conducted with parents, peer supporters and trainers. Interviews may be conducted in-person or by telephone. All interviews and focus groups will be audio recorded and take around 30-50 minutes.

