## 15.2 Sub-group analysis

Primary sub-group analysis will investigate the effect of ASSIST+Frank and Frank friends interventions on the frequency of any and specific drugs in a sub-group who report ever having used drugs at baseline. Exploratory sub-group analysis will investigate the association between the incidence of drug use and sex, family affluence, smoking status, and different peer social networks of tobacco and drug use.

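### Section 15.1 interacts allocation with post-randomisation changes in potential mediators, which estimates neither an indirect effect nor effect modification, and no section commits to allocation by friends' baseline substance use

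*Protocol*

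**What the plan says.** Section 15.1 (Main analysis) contains three relevant plans.

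- **Interactions with changes.** "We will model interactions between potential intermediary factors (e.g. changes in: the perceived prevalence of drug use within the year group". The bracketed list continues with knowledge, attitudes, drug offers, mental health and school engagement, and ends with "average level of drug use amongst peers; and average level of drug use amongst peer-leaders". Each is crossed with allocation in four contrasts: each active arm against usual care, and ASSIST against ASSIST+Frank. The section concedes low power but says the 95% intervals will show what effects are plausible in a full trial.
- **Mediator analysis.** "We will undertake mediator analysis to see if the identified pathways in the logic model are associated with the uptake of drug use".
- **Moderators.** The impact of demographic factors and "other theoretical moderators on the intervention effect using interaction terms" will be considered. Apart from demographics, no moderator is named.

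Section 8.3 says the attitudinal and knowledge data are collected to "explore potential mediators of the effect of ASSIST+Frank and Frank friends on drug use". Section 13.4 fixes the timing: "Baseline and 18-month follow-up self-report questionnaires will be completed under 'exam conditions". No survey is planned in between.

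Section 15.2 adds: "Exploratory sub-group analysis will investigate the association between the incidence of drug use and sex, family affluence, smoking status, and different peer social networks", and the sentence goes on to specify networks of tobacco and drug use. Its primary sub-group is students who had themselves used drugs by baseline.

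Section 4.1 describes an earlier peer-led trial in which an interaction between allocation and friends' substance use showed that "the intervention was most effective for students embedded in peer networks that did not engage in substance use", while students whose friends already used substances were more likely to increase their own use. Section 4.2 makes this possible harm part of the rationale.

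**The concern.** Moderation and mediation are different questions and need different terms. Moderation asks whether the effect of allocation differs between students who were already different at baseline. Mediation asks how much of the effect passes through something the intervention changes. Crossing allocation with a post-randomisation change answers neither. It asks whether the slope of outcome on change differs by arm, among students sorted by a variable that the intervention may have altered.

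This is a stated method, not a detail awaiting a SAP. The resulting intervals are meant to inform a later trial, and refining the logic model is a study objective (Section 5.2). A wrong estimand here could misdirect that work however cautiously it is reported.

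The harm signal in Section 4.1 is itself a moderation finding. Testing it requires friends' use at baseline, whereas the only explicit interaction on peer drug use is with its change.

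**Working it through.** The protocol gives no figure for these analyses, so there is none to reproduce. The check is algebraic, with simulations as illustration.

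**1. What the coefficient means.** Let A be allocation, M the intermediate and Y the outcome on a linear scale:

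- M = a0 + a·A + error
- Y = c0 + c·A + b·M + h·A·M + error

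If nothing confounds M and Y, the total indirect effect is a·(b + h). The planned interaction reports h.

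- If h = 0, the indirect effect is a·b, which can be the whole effect.
- If a = 0, the indirect effect is 0 whatever h is.

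So h is neither necessary nor sufficient for mediation. It can enter a mediation model as one component, but it is not the result.

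**2. Simulations.** Each used 400,000 individuals and logistic models without clustering. All coefficients are assumed; none comes from the protocol.

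*Case 1: full mediation, no interaction generated.* M = -0.8·A + noise; log-odds of Y = -2 + 0.8·M. The product a·b is -0.8 × 0.8 = -0.64. The fitted total log odds ratio is -0.61, and the interaction is 0.005 (SE 0.011). A milder set (a = 0.5 SD, b = -0.6, product -0.30) gives a total of -0.29, an odds ratio of exp(-0.29) = 0.75, with interaction -0.004.

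*Case 2: effect modified by friends' baseline use P0, true interaction 0.50.* Change D = r·P0 - 0.3·A + noise; log-odds of Y = -2 + 0.5·P0 - 0.3·A + 0.5·A·P0 + 0.3·D.

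| r | A × baseline | A × change (SE) | A × change, with P0 as a main effect |
|---|---|---|---|
| 0 | 0.49 | -0.02 (0.010) | -0.02 |
| -0.5 | 0.51 | -0.18 (0.009) | -0.19 |

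The baseline interaction recovers 0.50. The change interaction is near zero, or of the wrong sign when change regresses on baseline.

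*Case 3: allocation has no effect on the outcome.* A common cause U drives both variables, and its influence on M differs by arm: M = -0.3·A + (1 - 0.8·A)·U + noise; log-odds of Y = -2 + U. The total effect is -0.001. The interaction is -0.30 (SE 0.008), and the allocation coefficient in the same model is 0.18.

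**3. Where the harm question could be answered.**

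| Section | Peer-use variable | Crossed with allocation? | Baseline value? |
|---|---|---|---|
| 15.1, intermediates | Peers' and peer-leaders' drug use | Yes | No, listed under changes |
| 15.1, moderators | Not named | Yes | Not stated |
| 15.2, exploratory | Networks of tobacco and drug use | Not stated; worded as association with incidence | Not stated |
| 15.2, primary | Student's own use, not friends' | Intervention effect within sub-group | Yes |

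No row combines friends' substance use, allocation and baseline timing.

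**The case against.** Several points on the other side are sound.

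- **The interactions are not the only route to mechanism.** Section 15.1 plans a mediator analysis and also between-arm analysis of more immediate targets, such as knowledge and mean peer drug use. These are close to the two steps of a mediation analysis, and the choice of estimator can be left to a SAP. This stands, but it leaves the interaction sentence in place as a separate commitment.
- **The harm question is not shut out.** A reader might infer that the plan misses the signal from the earlier trial. The documents do not support that: the unnamed moderators could include friends' baseline use, and Section 15.2 names peer networks of tobacco and drug use. What remains is that no section commits to the specific interaction.
- **No decision hangs on it.** A reader might infer that a pathway with a null interaction would be dropped from the logic model. No such rule exists. P-values will not be presented, the progression criteria in Section 8.1 do not use these terms, and fidelity measures also feed the logic model (Section 13.3).
- **Case 1 generates no interaction, so it finds none.** That is so; it illustrates the algebra and is not independent evidence. In the milder set the allocation coefficient falls to 0.00 once the mediator is included, a pattern an analyst could notice. Case 3 shows why that coefficient is also unsafe: it is 0.18 when allocation has no effect on the outcome.
- **The analysis is exploratory and admittedly imprecise.** Imprecision is a different fault from estimating the wrong quantity. A wide interval around the wrong quantity still does not indicate a feasible effect size.

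**Conclusion.** The point holds in limited form. The allocation-by-change interactions in Section 15.1 should not be read as indirect effects or as effect modification, and their intervals should not be carried forward as plausible effect sizes for a full trial. This follows from the protocol's own description of the variables as potential mediators and from its two survey times; it needs no numerical assumption. The simulated values (about 0.00 under full mediation, -0.02 to -0.18 for a true baseline interaction of 0.50, and -0.30 under no effect) show what can happen under assumed inputs. They do not predict this trial's results.

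On harm, the finding is an omission of explicit commitment: allocation by friends' baseline substance use is permitted by the text but not named. The primary aim, the progression criteria and the main comparison of drug use between arms are unaffected.

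**What to change.** 1. **Section 15.1, interactions.** Limit interaction terms to baseline values, and name allocation by friends' baseline substance use. Define baseline as the survey that Section 9.6 places before randomisation; Section 13.5 words the timing differently and should be aligned.
2. **Section 15.2, exploratory sub-groups.** Word these as differences in intervention effect by baseline sex, family affluence, smoking status and friends' tobacco and drug use, not as associations with incidence.
3. **Section 15.1, mediator analysis.** Move the listed changes here. Estimate the effect of allocation on each 18-month intermediate, adjusted for its baseline value, and then the association of the intermediate with the outcome, adjusted for allocation and baseline. Report exploratory direct and indirect effects. An allocation-by-mediator term may be a component. State the assumption of no unmeasured mediator-outcome confounding, and that mediator and outcome are measured at the same survey.
4. **Intervals.** Apply the statement about feasible effect sizes only to the baseline interactions and to the direct and indirect effects, with those caveats.

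The cost is a change of wording and slightly more analysis; the network and drug-use questions are already planned (Section 8.3). The main limitation is precision. Section 4.2 reports, from an earlier feasibility trial, that few students aged 12 to 13 were experimenting with cannabis, so friends' drug use at baseline may vary little across 12 schools and the interaction may be very imprecise.

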## 15.2 Sub-group analysis

Primary sub-group analysis will investigate the effect of ASSIST+Frank and Frank friends interventions on the frequency of any and specific drugs in a sub-group who report ever having used drugs at baseline. Exploratory sub-group analysis will investigate the association between the incidence of drug use and sex, family affluence, smoking status, and different peer social networks of tobacco and drug use.

### 15.3 Qualitative analysis

We will aim for a maximum variation sample to achieve a broad perspective on the issues. The sampling criteria will be: school, trial arm, participant type (teacher, peer-supporter, pupil, parent) and gender. Emergent issues from earlier interviews and focus groups will be explored in subsequent interviews. We anticipate that 55 interviews will be undertaken, although this will depend on the depth and detail of information provided. All interviews will be recorded and transcribed verbatim. Analysis will be conducted using a structured thematic approach to systematically code, classify and organise interview content into key themes. Broad themes will then be broken down to identify commonly expressed themes and unusual cases. 10% of the data will be coded by two team members to check that the coding scheme is identifying all of the themes and concepts, and that there is a shared understanding of what

they are. Analysis will be conducted using QSR NVivo 10 software to assist systematic coding to identify emerging patterns between teachers, peer-supporters, pupils, parents and schools.

#### 15.4 Cost effectiveness analysis

To enable an economic evaluation to be conducted as part of a future definitive trial we will map in as much detail as possible the key cost and outcomes domains. This will include the costs of training the PHW trainers, the peer selection, recruitment and training, and follow-up sessions with peers. The provisional costs of running ASSIST+Frank and Frank friends have been calculated by PHW. We will identify any additional contributions by young people, parents, schools and other agencies to provide a more comprehensive estimate of cost. The extent to which these inputs can be translated into financial costs will be determined. The primary and secondary outcomes will be considered for their suitability as measures of output and outcomes for an economic evaluation. Cost effectiveness data may be used to inform the sample size calculation for a subsequent trial, if warranted.

### 16 Study closure

The end of the study/ will be considered as the date on which the last participant has completed their follow-up assessment.

## 17 Regulatory issues

# 17.1 Ethical and research governance approval

The study will be conducted in accordance with the recommendations for physicians involved in research on human participants adopted by the 18th World Medical Assembly, Helsinki 1964 and later revisions. The study has be granted ethical approval by Cardiff University School of Social Sciences Research Ethics Committee (Reference: SREC/ 1103). After consulting the Wales NHS REC, feedback was that NHS Research Ethics Committee approval for this study was not necessary. NHS R&D approval will however be sought.

#### 17.2 Consent

Schools

The head-teacher (or designated member of the school senior management team) will be asked to sign a formal commitment for their school to take part in the study. The commitment will describe the roles and responsibilities of the school and the research team during the research period at the school.

Teachers, parents and PHW staff

The ASSIST+Frank Study Manager will provide all adult participants with information on the study, explain the aims of the study and they will then be asked to give informed consent prior to participation in the research. They will be assured that if they decide not to participate, their decision will be handled confidentially. Written informed consent detailing the right to withdraw will be collected for all participants.

#### Student consent

Written consent will be sought from young people. Age-appropriate information sheets will be provided, together with verbal explanation by researchers. Parents who do not wish their child to participate will be able to 'opt-out'. Letters will be sent to parents/guardians to contact the school if they do not wish their child to participate in the trial. At the beginning of

data collections, it will be made clear that participation by students is optional. Note that this 'opt-out' consent is acknowledged standard practice for school-based studies in the UK, used by members of our investigator team in school-based interventions in England (e.g. Pupil-led sex education in England (RIPPLE study) (24)), and the original ASSIST RCT held in 59 schools (N students = 10,730) in South Wales and Bristol (10)).

